#### 1.1.2 Treatments for SEGA-associated with TSC

For SEGAs that exhibit serial growth, cause hydrocephalus, or produce any clinical symptoms, resection, until recently, was the only recommended treatment for these patients (Torres 1998, Sinson 1994, Cuccia 2003). The lack of reported spontaneous regression or subsequent stabilization in SEGAs supported this recommendation (Franz 2007). In addition, SEGAs do not typically respond to radiation therapy or chemotherapy (Franz 2007). Given

the genetic basis of TSC, the risk of inducing second malignancies through utilization of standard chemotherapeutic agents or radiation therapy has been noted ([Matsumura et al 1998](#)).

Everolimus first received accelerated approval from FDA on 29-Oct-2010 based on data from CRAD001C2485 under the trade name Afinitor® for the treatment of patients with SEGA associated with TSC who require therapeutic intervention but are not candidates for curative surgical resection based on data from CRAD001C2485. The effectiveness of Afinitor is based on an analysis of change in SEGA volume. Clinical benefit such as improvement in disease-related symptoms or increase in overall survival has not been demonstrated

Subsequently on 29-Aug-2012, the indication was revised by FDA based on results of study CRAD001M2301 and with the approval of the dispersible tablet to “Afinitor® Tablets and Afinitor® Disperz are indicated in pediatric and adult patients with TSC for the treatment of SEGA that requires therapeutic intervention but cannot be curatively resected. The effectiveness of Afinitor Tablets and Afinitor Disperz is based on demonstration of durable objective response, as evidenced by reduction in SEGA tumor volume. Improvement in disease-related symptoms and overall survival in patients with SEGA and TSC have not been demonstrated”.

In the EU, under the trade name Votubia®, everolimus first received conditional approval on 02-Sep-2011 based on the data from CRAD001C2485 for the treatment of patients aged 3 years and older with SEGA associated with TSC who require therapeutic intervention but are not amenable to surgery. Further clinical benefit, such as improvement in disease-related symptoms, has not been demonstrated. Based on data from CRAD001M2301, the European Commission decision was received on 15-Nov-2013 for removal of the age restriction and inclusion of the dispersible tablets.

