### **1.1.3 Growth and development**

#### **Growth**

Childhood growth and development are routinely monitored as part of child preventive health care in many countries. The assessment whether a child’s growth pattern deviates from that of the reference population is intended to detect childhood illnesses that manifest themselves through abnormal growth, ideally before any other signs or symptoms of the disease have appeared.

Close monitoring of growth and development may be even more important when children are treated over long periods of time with drugs like everolimus that interfere with complex intracellular signaling pathways. Everolimus is an inhibitor of mTOR, a key player in a multifunctional, intracellular signal transduction pathway which has been shown to be essential for various vital processes. mTOR senses cellular nutrient and energy levels, and is one of many regulators of the cell cycle and proliferation. At present, it is unknown if long term treatment with everolimus affects the growth and development of children. Under certain circumstances everolimus is the only treatment option for children with SEGA associated with TSC. In this study, the height and weight for BMI of pediatric patients who take or have taken everolimus will be assessed on an annual basis to detect possible abnormalities.

WHO (World Health Organization) growth charts and other population-specific growth data have been used to establish cut-off values that define abnormal growth. The most commonly used parameter is height-for-age [expressed as height SD score (SDS) or height percentile].

Standard deviations scores (SDS) give an indication of the stature of the subject relative to a normal population of that age, a value of 0 being average and + and - values representing degrees of tallness and shortness, respectively.

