## **10.1 Analysis sets**

### **10.1.1 Full Analysis Set**

In order to describe data from the CRAD001M2305 patients and those from the TOSCA registry side by side, the following analyses sets will be used.

- The Full Analysis Set (FAS):
  - for CRAD001M2305, FAS will consist of all patients enrolled in this study.
  - for TOSCA, FAS will consist of all patients enrolled in this TOSCA registry whose age at study entry was below 17 years and who never received an mTOR inhibitor throughout the registry follow-up period.
- The Full Analysis Set for sexual development (FAS Puberty):
  - for CRAD001M2305, FAS Puberty will consist of the FAS patients defined above.
  - for TOSCA, FAS Puberty will consist of the FAS patients defined above but restricting from the patients to those aged between 9 to 17 years at study entry. The TOSCA registry is designed to collect Tanner Staging until 2017 (i.e. 4 to 6 years of follow-up). Thus it is considered adequate to select only TOSCA patients aged between 9 to 17 years old at the time of entry to the registry to allow for obtaining puberty data corresponding to the peri-pubertal time frame.

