TAND	TSC-Associated-Neuropsychiatric-Disorders
TSC	Tuberous Sclerosis Complex
VAP	Validation and Planning

1 Introduction

This Statistical Analysis Plan (SAP) is for the evaluation of the long-term follow-up study to monitor the effect of everolimus on the growth and development of pediatric patients previously treated with everolimus in study CRAD001M2301 (EXIST-LT). Statistical analyses will be primarily descriptive for all endpoints. The planned statistical analysis is described in Section 10 of the protocol.

The data will be analyzed by Novartis.

Data collected in this CRAD001M2305 study will be pooled with the corresponding data collected in the parent CRAD001M2301 study, in particular, background information on the disease history, demographics and baseline characteristics, everolimus exposure, sexual and growth development data.

This pooling will allow for the following:

- Obtaining baseline values collected in CRAD001M2301 before start of everolimus
- Calculating the whole exposure to everolimus for patients enrolled in the CRAD001M2305 study
- Considering the whole growth/development course over time from the start of everolimus.

The data of the patients enrolled in the CRAD001M2305 study and a subset of patients who were never exposed to any mTOR inhibitors on the CRAD001MIC03 study (TOSCA, and these patients are referred to as TOSCA patients) will be presented, side by side, whenever similar data were collected in both studies. This is intended to facilitate the interpretation of the CRAD001M2305 results and help differentiate the impact of the TSC condition versus any potential impact of everolimus on growth and sexual development.

If the missing data pattern is not limiting and if the number of patients in each study is sufficient, exploratory indirect comparisons between patients treated by everolimus (enrolled in CRAD001M2305 study) and patients who were never exposed to any mTOR inhibitors (TOSCA patients) will be performed to evaluate the everolimus effect on growth and sexual development.

2 Definitions and general methodology

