2.3.1 Full Analysis Set

In order to describe data from the CRAD001M2305 patients and those from the TOSCA registry side by side, the following analysis sets will be used.

- The Full Analysis Set (FAS):
 - for CRAD001M2305, FAS will consist of all patients enrolled in the CRAD001M2305 study.
 - for TOSCA, FAS will consist of all patients enrolled in this TOSCA registry whose age at study entry was below 16 (for female) and 17 (for male) years and who never received an mTOR inhibitor throughout the registry follow-up period nor recorded as prior or ongoing treatment at the baseline visit.
- The Full Analysis Set for sexual development (FAS Puberty):
 - for CRAD001M2305, FAS Puberty will consist of the FAS patients defined above.
 - for TOSCA, FAS Puberty will consist of the FAS patients defined above but restricting from the patients to those aged between 9 to 17 years (for, females 9 to 16 years, males 9 to 17 years) at registry entry. The TOSCA registry is designed to collect Tanner Staging until 2017 (i.e. 4 to 6 years of follow-up). Thus it is considered adequate to select only TOSCA patients aged between 9 to 17 years old at the time of entry to the registry to allow for obtaining puberty data corresponding to the peri-pubertal time frame.

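### The TOSCA reference set is selected on treatment started after registry entry, which may tilt it toward milder TSC by an unknown, possibly zero, amount

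*SAP*

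**What the plan says.** SAP 2.3.1 limits the TOSCA Full Analysis Set, beyond an age limit, to patients "who never received an mTOR inhibitor throughout the registry follow-up period". It also excludes anyone with such a drug "nor recorded as prior or ongoing treatment at the baseline visit". Protocol 10.1.1 carries the same follow-up condition: "whose age at study entry was below 17 years and who never received an mTOR inhibitor throughout the registry follow-up period". The puberty set is a subset, bounded by age in years when the patient joined the registry: "for TOSCA, FAS Puberty will consist of the FAS patients defined above but restricting from the patients to those aged between 9 to 17". The same section puts the registry's Tanner follow-up at 4 to 6 years.

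SAP 2.1.3 sets TOSCA study day 1 at enrollment, and SAP 2.1.6.1 builds yearly windows from that date. No section keeps the untreated data of a patient who starts an mTOR inhibitor later, or censors at the start. SAP 3.8.4, on missing values and censoring, has no such rule.

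SAP Section 1 gives the purpose of the side-by-side display: to "help differentiate the impact of the TSC condition versus any potential impact of everolimus on growth and sexual development".

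**The concern.** Entry into the reference depends on something not known at time zero. A Year 1 height SDS counts only if the child starts no mTOR inhibitor in any later year. The baseline exclusion of prior or ongoing users is different: it is known at entry and is legitimate for an untreated reference.

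The likely direction comes from the indication. Protocol 1.1.2 describes everolimus as indicated "for the treatment of SEGA that requires therapeutic intervention but cannot be curatively resected", and Protocol 1.1.3 adds: "Under certain circumstances everolimus is the only treatment option for children with SEGA associated with TSC". Later starters may therefore be the TOSCA patients most like those in CRAD001M2305, all of whom had TSC-associated SEGA and received everolimus in the parent study. The rule also favours patients with short follow-up, who have less time in which to start.

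What is at stake is attribution. If later starters do less well while untreated, removing them makes TSC look more benign and moves part of any CRAD001M2305 deficit onto everolimus. SAP 2.2 acknowledges that growth in TSC without mTOR inhibitors is poorly characterized, so TOSCA is the plan's only untreated TSC reference. Nothing in the display would reveal the selection.

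**Working it through.** **The plan's own figures.** The documents give no figure for this selection. The nearest is the precision table in SAP 4.2, which reproduces: the exact binomial 95% interval for 1/15 is (0.002, 0.319), printed there as (0.00, 0.32).

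**Inputs that the documents do not give (assumptions)**
- f, the share of otherwise eligible TOSCA patients who start an mTOR inhibitor during follow-up: 10-30%.
- d, how much lower the mean untreated height SDS of later starters is than that of never-users: 0-0.8. Zero must be included, because no section says that they differ.

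**Shift in the mean at baseline.** If all patients mTOR-naive at entry are kept, the mean is (1 - f) x m + f x (m - d) = m - f x d, where m is the never-user mean. The never-exposed set is therefore too high by f x d:
- d = 0: no shift for any f.
- f = 0.10, d = 0.8: 0.08 SDS.
- f = 0.30, d = 0.8: 0.24 SDS.

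**How much the fix recovers in later windows.** Assume in addition that starts are uniform over 5 years. Later starters still untreated at year t then make up f(1 - t/5) / [1 - f + f(1 - t/5)] of the set. The difference between the two versions of the reference is that share times d. With d = 0.8:

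| Year | Share, f = 0.10 | Difference (SDS) | Share, f = 0.30 | Difference (SDS) |
|---|---|---|---|---|
| 0 | 10.0% | 0.08 | 30.0% | 0.24 |
| 1 | 8.2% | 0.07 | 25.5% | 0.20 |
| 2 | 6.2% | 0.05 | 20.5% | 0.16 |
| 3 | 4.3% | 0.03 | 14.6% | 0.12 |
| 4 | 2.2% | 0.02 | 7.9% | 0.06 |

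Worked entry, f = 0.30 at year 3: 0.30 x 0.4 = 0.12; 0.12 / (0.70 + 0.12) = 0.146; 0.146 x 0.8 = 0.12.

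**Untreated person-time discarded.** Under the same uniform-start assumption this is 2.5f / [5(1 - f) + 2.5f]: 5% for f = 0.10, 11% for f = 0.20 and 18% for f = 0.30.

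**Shift in the abnormality rate.** Let r be the never-user rate and k the ratio of the later starters' untreated rate to it. The shift is f x (k - 1) x r. I take r = 5-10%, the parent-study range in SAP 3.13, only to set the scale, and assume k = 1-3.
- k = 1: 0 points.
- f = 0.20, k = 2: 1-2 points.
- f = 0.30, k = 3: 3-6 points (for example, 10% becomes 16%).

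**Comparison with the precision in CRAD001M2305.** The 1/15 interval spans about 32 points. With an assumed SDS standard deviation of 1, the standard error of a mean of 15 is 1/sqrt(15) = 0.26, and the 95% half-width is about 2.14 x 0.26 = 0.55. The largest illustrated shift, 0.24, is below one standard error.

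**The case against.** The strongest reply is that the bias is inferred. The documents show who receives everolimus. They do not show that later starters are shorter, have a different BMI or mature later while untreated. Protocol 2.1 says only that TSC and SEGA could possibly affect growth and sexual development. This stands: a reader might infer that the reference is demonstrably too healthy, or that everolimus is being made to look worse, and the documents support neither as fact.

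A reader might also infer that setting aside the propensity-score comparison in SAP 4.2 removed the correction. It did not. That method worked within the TOSCA analysis sets and could not have restored patients already excluded from them.

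The remedy has its own weaknesses. If patients start because their disease worsens, censoring at the start is informative. Starters leave successive yearly windows, so the make-up of the reference drifts in a way that the present rule avoids. These points stand and should be stated with the results; they are a reason to show both sets.

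Other replies carry less weight. The untreated reference was a deliberate addition in Amendment 1, but choosing an untreated reference does not require defining it by later treatment. SDS is anchored to WHO charts, but those cannot separate TSC from everolimus. No tests are planned on rates and the intervals are wide, but imprecision in CRAD001M2305 does not remove a systematic shift in the reference. The SAP's cautions about observational data and unobserved covariates do not mention this selection.

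**Conclusion.** The selection on later treatment is explicit in both documents and reaches both TOSCA analysis sets. That it may tilt the reference toward milder TSC is a reasonable inference from the indication. Whether it moves height, BMI or puberty results is unknown.

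Under the stated assumptions the baseline mean SDS is 0-0.24 too high and the abnormality rate 0-6 points too low. Neither range is an estimate. The effect is on how a descriptive display is interpreted, not on a test or a sample size. The change is justified because it costs little and either removes or exposes a selection in the one comparison meant to separate TSC from everolimus. It would not make the groups comparable: CRAD001M2305 patients all have SEGA, while the TOSCA set is not restricted to SEGA.

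**What to change.** In SAP 2.3.1:
- Define the TOSCA FAS by mTOR-naive status at registry entry, with the present age limits, and let FAS Puberty follow from it.
- Use each patient's data up to the first mTOR inhibitor dose or, if the start date is not recorded, up to the last visit before use is first reported.
- Show this set side by side with the existing never-exposed set.
- Report the number and baseline characteristics of later starters.

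Endpoint rules:
- Ages at Tanner stages: Kaplan-Meier with censoring at the start.
- Tanner V by 16 (females) or 17 (males): the Kaplan-Meier estimate at that age, because patients who start earlier have no untreated outcome. SAP 3.9.2 already plans a Kaplan-Meier analysis of age at Stage V, so the same estimate can be given for CRAD001M2305.
- Height and BMI abnormality rate: the last untreated value.

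State with the results that censoring at the start may be informative, that the make-up of the yearly windows changes as starters leave, that some patients contribute shorter follow-up, and that TOSCA is not restricted to SEGA.

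The cost is SAP wording, one cutoff date per later starter and one more display. The present rule already requires knowing who used an mTOR inhibitor during follow-up. The documents do not show whether start dates are held, and TOSCA growth data are annual only where available, so the recovered data may be sparse. If the sponsor keeps the present set alone, it should at least report how many patients were excluded for later use.

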## 4 Study design

### 4.1 Description of study design

This is a prospective, multi-center, long-term follow-up, Post-Authorization Safety Study (PASS) evaluating the growth and development of pediatric patients who are currently being treated with everolimus or who have previously been treated with everolimus for TSC-associated SEGA in [CRAD001M2301]. The study will include all consenting pediatric patients who at the time of completion of study CRAD001M2301 have not achieved Tanner Stage V and are younger than 16 years (for females) or 17 years (for males), and were receiving treatment with everolimus in study [CRAD001M2301] within 6 months before enrollment into CRAD001M2305.

According to [CRAD001M2301] enrollment figures, it is anticipated that at the time of the start of study CRAD001M2305, approximately 50 patients may be eligible for this study, if they consent to participate.

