# 5 Population

## 5.1 Patient population

The target population is comprised of pediatric female and male patients who have previously participated in the study [CRAD001M2301] and have not, prior to enrollment into CRAD001M2305, reached age 16 for females, or age 17 for males. Additionally, these patients will not yet have achieved Tanner Stage V. Study treatment in study [CRAD001M2301] must have been completed within 6 months prior to enrollment into CRAD001M2305.

The investigator or designee must ensure that only patients who meet all inclusion are offered participation in the study. No additional exclusions can be applied by the investigator, in order that the study population will be representative of all eligible patients. All screening assessments must be completed and reviewed by the investigator (or designee) prior to starting study participation in CRAD001M2305.

All pediatric study patients and their parent(s) or legal guardian must be thoroughly informed about all aspects of the study, including the study visit schedule and required evaluations, and all regulatory requirements in order to ensure informed consent. The written informed consent must be obtained prior to performing any CRAD001M2305 study procedures. If the patient is unable to read, an impartial witness and/or the patient's parent or legal guardian must be present during the entire informed consent discussion. The following criteria apply to all patients enrolled into the study.

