## 5.2 Inclusion criteria

Patients eligible for inclusion in this study have to meet **all** of the following criteria:

1. Pediatric female patients who were on study treatment in study [CRAD001M2301] within the past 6 months and have not reached Tanner Stage V or age 16 at the time of

completion of [CRAD001M2301]  
or

2. Pediatric male patients who were on study treatment in study [CRAD001M2301] within the past 6 months and have not reached Tanner Stage V or age 17 at the time of completion of [CRAD001M2301].
3. Written informed consent according to local guidelines.

Tanner Staging results that were obtained and documented within 6 months prior to enrollment into CRAD001M2305 may be used for enrollment decisions.

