3.9.2 Other safety data

For CRAD001M2305 patients, all data described below will be pooled with the corresponding data from Study CRAD001M2301 **except** for the TAND checklist as this assessment was not collected in the parent study CRAD001M2301.

The other secondary objectives of the study will be based on sexual and neuropsychological (TAND checklist) development data.

The age when patients reach each Tanner Stage II-V will be summarized on the FAS Puberty of Studies CRAD001M2305 and TOSCA.

The following variables will be summarized on the Safety Set (those are only collected in the CRAD001M2305 study) using descriptive statistics:

- age when females will start thelarche
- age when females will have their first menses
- age when males will reach adrenarche

For the age at which Tanner Stage II will be achieved, summary statistics from the KM distribution will be determined on the FAS puberty, including the median age and the proportions of patients reaching this milestone at some given ages. These statistics will be given as point estimates with 95% confidence intervals. The same analyses will be performed for the following variables: age at which each Tanner Stage III, IV and V will be reached. Age at thelarche (females), age at menarche (females) and age at adrenarche (males) will be described similarly on the SS.

Potential delayed puberty will be defined based on Tanner stage and also on onset of menarche for girls. Potential cases identified through this algorithm, will be then clinically reviewed by assessing all available information in order to conclude the clinical relevance of the delay.

Potential delayed puberty in girls is defined as failure to attain Tanner Stage II (for both breast development and pubic hair) by age 13, or absence of menarche by age 15 or within 5 years of attainment of Tanner Stage II [Fenichel 2012] Potential delayed puberty in boys is defined as failure to attain Tanner Stage II (for both testis and pubic hair) by age 14 ([Traggiai 2002], [Tanner 1962])

Rates of potential delayed puberty will be described for boys and girls separately among the patients at risk of delayed puberty along with 95% confidence intervals. The patients at risk are patients who may potentially present an event of potential delayed puberty at baseline.

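### M2305 enrols only children not yet at Tanner Stage V and TOSCA does not, so the side-by-side Stage V results need a delayed-entry analysis and cannot be read as a drug effect

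*SAP*

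**What the plan says.** **M2305 entry.** Protocol 4.1 admits children who, when the parent study ended, "have not achieved Tanner Stage V and are younger than 16 years (for females) or 17 years (for males"). Protocol 5.2 words it for boys as "have not reached Tanner Stage V or age 17 at the time of completion of [CRAD001M2301"], with the same rule for girls at 16. Protocol 5.1 says of the target population: "Additionally, these patients will not yet have achieved Tanner Stage V". SAP 2.3.1 then states: "for CRAD001M2305, FAS Puberty will consist of the FAS patients defined above". Nobody in the M2305 puberty set should therefore have been at Stage V on enrolment.

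**TOSCA entry.** SAP 2.3.1 takes registry patients "whose age at study entry was below 16 (for female) and 17 (for male) years" who never received an mTOR inhibitor. It forms the puberty set by "restricting from the patients to those aged between 9 to 17 years" (females to 16). Neither step mentions Tanner stage, and Protocol 10.1.1 has the same gap. The same SAP section says the registry is "designed to collect Tanner Staging until 2017 (i.e. 4 to 6 years of follow-up").

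**Analyses.** SAP 3.8.2 puts the percentage at Stage V by 16 (females) or 17 (males) side by side for the two sets. SAP 3.9.2 summarises age at Stages II to V in both studies. For Stage II, "summary statistics from the KM distribution will be determined on the FAS puberty", and the same is planned for Stages III to V. SAP 2.4.3.1 names the ordinary product-limit estimate in PROC LIFETEST, without delayed entry. SAP 3.1 makes the relevant population the denominator of percentages, and SAP 3.8.4 shows missing outcomes as missing.

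**The concern.** A child who reached Stage V on everolimus before M2301 ended cannot appear in M2305. An equally mature TOSCA child under 16/17 at registry entry stays in and, since nothing says otherwise, counts as having attained Stage V. M2305 is thus left-truncated at enrolment age and the TOSCA set is not.

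The ordinary Kaplan-Meier estimate starts every M2305 patient at birth. It credits them with event-free years in which the event was impossible, because having it would have kept them out of the study. Pooling M2301 data does not help, since only patients who later enrolled in M2305 contribute.

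Stage V by 16/17 is a primary endpoint (Protocol 3). SAP 1 says the side-by-side display is there to help separate the effect of the disease from that of the drug. Delayed maturation is the signal of interest, and this entry rule can imitate it.

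**Working it through.** **1. The plan's own figures.** The documents give no size for this effect. Their only precision figures are exact binomial intervals for growth abnormality. SAP 4.2 prints (0.60, 0.98) for 13 of 15, and recalculation gives 0.595 to 0.983. That is the precision available with 15 patients.

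**2. The selection effect alone.** Let F be the distribution of age at Stage V, the same in both studies (no drug effect). Let L be the age limit and *a* the entry age. For a child enrolled only if not at V at *a*:

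P(V by L | not V at *a*) = (F(L) − F(*a*)) / (1 − F(*a*)), which never exceeds F(L).

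Assumed for illustration (not in the documents): F normal, mean 1.5 years before L, SD 1.25. Then F(L) = Φ(1.5/1.25) = Φ(1.2) = 0.885.

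| Entry before L | F(*a*) | P(V by L), M2305 |
|---|---|---|
| 7 years | 0.000 | 88.5% |
| 4 years | Φ(−2.0) = 0.023 | (0.885 − 0.023)/0.977 = 88.2% |
| 2 years | Φ(−0.4) = 0.345 | (0.885 − 0.345)/0.655 = 82.4% |
| 1 year | Φ(0.4) = 0.655 | (0.885 − 0.655)/0.345 = 66.6% |

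**3. Averaged over entry ages.** This was simulated with no drug effect, one pooled limit of 16.5, and a mean 1.0 to 2.0 years before the limit with SD 1.0 to 1.5. M2305 entry was uniform from 4, 7 or 10 years up to 3 months before the limit, with complete follow-up. The M2305 percentage is about 0.3 to 5 points low and the ordinary Kaplan-Meier median about 0.1 to 0.4 year late.

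**4. The opposing effect.** With 6 years of TOSCA follow-up, a boy entering before 11 (17 − 6) or a girl before 10 (16 − 6) is never observed to the limit. With 4 years the cut-offs are 13 and 12. Under the SAP 3.1 denominator these children stay in the divisor without being seen to reach V by the limit, unless they mature early. With TOSCA entry uniform from 9 to the limit:

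| TOSCA handling | TOSCA | M2305 | Appearance |
|---|---|---|---|
| Unobserved outcomes dropped | 79–98% | 70–97% | M2305 later |
| Whole-set denominator, 4–6 years | 64–89% | 70–97% | M2305 earlier in every scenario |

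Medians are also conditional. TOSCA children already at V have no observed attainment date. If they are dated at first assessment, the TOSCA median is 0.2 to 0.5 year late and the order usually reverses.

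**5. Dropping TOSCA patients already at V.** Mean 1.5 years before the limit, SD 1.25, M2305 entry from age 4 (M2305 = 87.1%):
- Complete follow-up: TOSCA falls from 88.4% to 85.4%. The gap goes from 1.3 points to 1.7 points in the opposite direction.
- 4–6 years, whole-set denominator: TOSCA falls from 77.3% to 71.3%. The gap widens from 9.8 to 15.8 points.

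This happens because TOSCA starts at age 9 and M2305 has no minimum age, so the same exclusion bites harder in TOSCA.

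**6. Delayed entry.** Each patient enters the risk set at entry age and is censored at last observation. This recovered the true median and the true percentage by the limit, in both sets, in every scenario run. The ordinary M2305 median was 0.07 to 0.45 year late in the same runs.

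**The case against.** A reader might infer that the entry rules bias the comparison against everolimus, so that M2305 will look later-maturing than TOSCA. The documents do not support that. The registry's short Tanner follow-up, combined with the whole-set denominator, reversed the percentage comparison in every scenario run, and the order of the medians depends on an unstated dating rule. Only the component in step 2 has a certain sign.

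It is also fair to say that the effect may be small here. Protocol 2.1 describes patients with this condition as typically pre-pubertal, and the documents give no entry-age distribution. An exact interval about 38 points wide at 13 of 15 dwarfs an average shift of at most 5 points. The plan is primarily descriptive, SAP 2.4.2.1 plans no tests on percentages, and SAP 4.2 calls 15 patients too few for any comparison. These points limit the weight of the issue. They do not remove it, because the side-by-side display stays.

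Nor does another planned analysis correct it. Baseline Tanner stage is a covariate only in the indirect comparison of SAP 3.9.3, which SAP 4.2 judges not meaningful. M2305 baseline is normally the start of everolimus (SAP 2.1.4), or for some patients the first later Tanner assessment (SAP 2.1.5). Adjusting for it would not reproduce the rule applied at M2305 entry.

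Finally, truncation acts directly only on Stage V. Stages II to IV are affected indirectly.

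**Conclusion.** The point stands in a limited form. The two puberty sets are selected differently on the outcome being compared, and the planned Kaplan-Meier method ignores it. Taken alone, this makes M2305 look later-maturing by about 0.3 to 5 percentage points and 0.1 to 0.4 year in the median. The loss is far larger for a child enrolled within a year or two of the limit and nearly nil for one enrolled well before puberty. These sizes rest on assumed normal ages at Stage V and uniform entry ages.

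The net direction of the displayed difference is undetermined, because TOSCA's follow-up and the denominator work the other way on the percentage. An opposing error of unknown size is not a correction, so neither crude comparison should be read as a drug effect. This should be fixed in the SAP. It does not invalidate the study.

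**What to change.** For Stage V only, amend SAP 2.4.3.1 and 3.9.2:

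- Use Kaplan-Meier with delayed entry: age at M2305 enrolment for M2305, age at registry entry for TOSCA, censoring at the last Tanner assessment. Patients already at V at entry do not enter the risk set.
- In SAP 3.8.2, report the percentage at V by 16 (females) or 17 (males) for both sets from this same estimate, beside the crude percentage.
- Do not simply remove TOSCA patients at V from the crude percentage; step 5 shows that this can widen the spurious gap.
- Footnote the tables: entry rules and follow-up differ, so the crude side-by-side figures are not a drug effect.

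Delayed entry assumes that, apart from the entry rule, entry age is unrelated to age at Stage V. The SAP should say so.

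The cost is SAP wording and one entry-age variable, with no new data collection. With about 15 M2305 patients the early risk sets are small and the intervals wide, and TOSCA patients already at V contribute nothing to this estimate.
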